4 TREATMENT PLAN

4.1 Subject Status Definitions

Enrolled: All subjects who sign an informed consent will be considered enrolled on the study.

Screen Failure: A subject who is withdrawn or discontinues from the study prior to receiving any protocol therapy (genistein or placebo) is considered a screen fail. Screen failures do not count toward accrual and will be replaced.

On Study: An enrolled subject is considered on-study/registered when a site investigator has determined that the subject has met all of the inclusion and none of the exclusion criteria, and the Study Chair, Study Research Coordinator, or designee has confirmed the eligibility. The on study date is the date that eligibility is confirmed at UVa.

Randomized: A subject that has been assigned to an arm is considered randomized.

On Treatment: A subject is considered on-treatment on the date that the protocol therapy (genistein/placebo) is initiated (i.e. Cycle 1 Day 1).

Off Treatment: The off-treatment date is the date that the subject, for any reason, is no longer receiving protocol therapy (genistein or placebo). It begins the day after the last dose of study supplement.

On Follow-up: A subject is considered on follow-up on the date that the protocol therapy is completed or discontinued for any reason listed in [Section 4.9](#). The on follow-up date is described below.

- Protocol therapy completed per protocol: date after Cycle 4 Last Day, same as off-treatment date
- Early discontinuation of protocol therapy: same as off-treatment date
- Screen failure: date determined to be ineligible

Off Follow-up: A subject is considered off follow-up when he or she has completed the follow-up period or the last date of follow-up if withdrawn during this period

Off-Study: A subject is considered off-study if he or she is removed from the study for any of the reasons listed in [Section 4.10](#) or if he or she has completed follow-up. It begins the date that the subject's participation in protocol activities has ended and typically coincides with the off-follow-up date.

- Follow-up period completed per protocol: date of six months post-treatment review
- Screen failure: date determined to be ineligible
- Withdrawn from study: date withdrawn

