4.9 Discontinuation of Protocol Therapy

Subjects will receive genistein or placebo for four 14- or 21-day cycles of chemotherapy, depending upon chemotherapeutic regimen, or until any of the following occur:

- Development of a secondary condition which, in the investigator’s opinion, would compromise patient safety or study results
- A female subject becomes pregnant
- Non-compliance with study procedures or protocol therapy (missing more than 20% of prescribed doses of genistein/placebo) since the first dose of study supplement treatment
- Consumption of prohibited soy-based products more than once during the Treatment Phase ([Section 4.8.1](#))
- Unacceptable AE(s). Subjects who experience [National Cancer Institute \(NCI\) Common Terminology Criteria for Adverse Events \(CTCAE\) Version 4](#) grade 3 or higher AE that is possibly, probably, or definitely related to the genistein/placebo during Cycle 3 or 4
- Chemotherapy regimen is altered such that it no longer meets Inclusion Criterion #5 ([Section 3.1](#))
- Subject’s treatment assignment is unblinded ([Section 4.6](#))
- Subject decides to discontinue protocol therapy

If a subject discontinues protocol therapy for any of the above reasons, the subject will be considered “Off-treatment” and the subject will be “On Follow-Up”. Subjects removed

from protocol therapy for (an) unacceptable AE(s) will be followed until resolution or stabilization of the AE.

Should a pregnant subject consent, the subject will also be followed to determine the outcome of her pregnancy (including any premature termination of the pregnancy). Generally, follow-up will be requested by the Sponsor no longer than 8 weeks following the delivery or termination date.

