6 EVALUATIONS AND ASSESSMENTS

6.1 Study Procedures and Assessments Table

Table 3: Schedule of Events

Assessment ¹	Pre-Treatment	Treatment Phase				Follow-up ²
	Day -28 to Day 1 ³	Cycle 1 Day 1 ^{3,4}	Cycles 1 - 4 Weekly ⁵	Cycles 2 - 4 Day 1	Cycle 4 Last Day ⁶	
Informed Consent	X					
Eligibility Determination	X					
Baseline ⁷ and Demographic ⁸ Data	X					
Randomization ⁹	X					
Medical History/Baseline Condition	X					
Physical Exam ¹⁰	X	X	X	X		
Height and Weight		X		X		
Chemistry/Metabolic Panel ¹¹	X	X		X		
CBC with Differential ¹²	X		X	X		
CRP, ESR, and Homocysteine ¹³	X			X	X	
Cytokine and Isoflavone Panels ¹⁴		X		X	X	
Audiogram ¹⁵	X			X	X	
Concomitant Medications Review ¹⁶	X ¹⁷	X	X	X	X	
Adverse Events Review		X	X	X	X	X
Study Medication Dispensing		X		X		
Subject Pill Diary ¹⁸		X	X	X	X	
Study Medication Reconciliation				X	X	

¹ All visits and assessments must be completed within ± 72 hours of the milestone date unless otherwise specified.

² Subjects must be followed for 30 days following the last study intervention for AEs and for 6 months for SAEs, unless consent is withdrawn.

³ Cycles begin on Day 1. There is no Day 0.

⁴ Cycle 1 Day 1 assessments do not need to be repeated if completed in the 7 days prior (i.e. Day -7 to Day 1) unless otherwise stated.

⁵ Weekly visits are to occur at 7-day intervals between Day 1 and the cycle's last day.

⁶ The last day of a cycle corresponds to the Day 1 of the next cycle. The last day's number will vary by cycle length.

⁷ Diagnosis, stage, grade, site(s) of disease, anti-neoplastic treatment +/- radiation regimen

⁸ Age, sex, race, and ethnicity

⁹ Randomization must occur within the 2 days prior to the anticipated Cycle 1 Day 1. ([Section 4.5](#))

¹⁰ Full physical exam at the beginning of each cycle of chemotherapy, and a symptom-directed physical exam at each of the weekly treatment visits. Collect height, weight and BSA on Day 1 of each cycle.

¹¹ Chemistry labs to assess for general safety must be conducted on Day 1 of each cycle. They must include serum creatinine, total bilirubin, AST, and ALT.

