6.4 Post-Treatment/Follow-up Assessments

All subjects will be followed for a minimum of 30 days after the last dose of protocol therapy (genistein/placebo) to assess for AEs. If subjects complete all four cycles of anti-neoplastic therapy, this visit will occur at 35 ± 5 days following the last day of Cycle 4. If subjects are withdrawn or discontinued prior to completion of the anti-neoplastic therapy, this will occur at 35 ± 5 days following the last day the study supplement is administered.

All serious adverse events (SAEs), other grade 3 – 4 AEs that are believed to be related to the investigational intervention, cancer progressions and relapses (including date, description, and sites), secondary malignancies (including date, description, and sites), and deaths (with date and clinical narrative) must be reported until 6 months after the end of the study intervention. See [Section 9.2](#) for additional information on AE and SAE reporting during this period.

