9.1 Definitions

9.1.1 Adverse Event [72]

An adverse event is any untoward medical occurrence in a subject who has received an investigational intervention, whether or not related to the investigational intervention(s). Medical conditions present before starting the investigational intervention (pre-existing conditions) will be considered AEs only if they worsen after starting the study supplement ([Sections 6.3](#) and [9.1.6](#)). AEs include unfavorable, harmful or pathological changes in the general condition of a subject; subjective or objective symptoms (spontaneously offered by the subject and/or observed by the Investigator or the study nurse); intercurrent events or exacerbation of pre-existing diseases which occurred after the administration of the study supplement; clinically significant changes in laboratory abnormalities; or any undesirable and unintended effect of research occurring in human subjects as a result of the collection of identifiable, private information for research purposes.

Only clinically significant AEs will be reported on this study. Reporting will include, at minimum, the dates of onset and resolution, severity, attribution to study intervention, expectedness, seriousness, and treatment (medication, transfusion, procedure, other, or none). AEs should be reported as diagnoses, when possible.

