9.2 Required Reporting

9.2.1 UVa Cancer Center DSMC Reporting Requirements

All AEs must be reported into UVa Cancer Center OnCore database within the time frame specified below. All timeframes are expressed in (calendar) days from the first point at which any member of the study team learned of the event.

For the purposes of reporting AEs for DSMC review, expectedness is defined in relationship to treatment with the investigational agent. I.e. Is the AE in question expected when undergoing genistein treatment? See Sections [5.1.7](#) and [5.2.4](#) for the expected AE. AEs meeting the thresholds below require additional reporting in OnCore beyond the routine data capture associated with a reporting period.

Target AEs do not need to be reported apart from routine data capture unless they meet the criteria below. Progressions, recurrences, and secondary malignancies must be reported within 30 days of the end of the reporting period during which they occurred, or the next quarterly deadline, whichever comes last. See the Procedure Manual for additional information pertaining to data capture.

Table 5. DSMC reporting requirements for AEs that occur during Cycles 1 – 4

Attribution to Study Supplement	Grades 1 & 2		Grade 3		Grade 4	Grade 5
	Expected & Unexpected		Expected & Unexpected		Unexpected	Unexpected
	Target AEs ¹	All other:	Target AEs ¹	All other:		
Unrelated	OnCore: 30 days/quarterly ³	Not required	OnCore: 30 days/quarterly ³	Not required	OnCore: 30 days/quarterly ³	See SAE
Unlikely				OnCore: 30 days from end of Cycle		
Possible				OnCore: 15 days from end of Cycle		
Probable						
Definite						
SAE ⁴	OnCore: (24-hrs), 7 days ²					

¹ Target AEs: Neutrophil count decreased, infection (any), mucositis oral, febrile neutropenia, fever, tinnitus & hearing impaired (subjects on platinum-based chemotherapy only), peripheral

motor neuropathy (subjects on vincristine only).
² Enter into Cancer Center database within 24 hours and submit supporting documentation within 7 days.
³ Data to be entered within 30 days of the end of the reporting period or the next quarterly deadline, whichever comes last. Deadlines are Jan. 31, Apr. 31, July 31, and Oct. 31.
⁴ Any AE that is an SAE must be reported using the SAE timeline regardless of grade or attribution.

Less stringent reporting is required during the follow-up period.

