Table 6. DSMC reporting requirements for AEs that occur after the subject’s last cycle taking the study supplement until 6 months post-treatment (i.e. follow-up)

Attribution to Study Supplement	Grades 1 & 2	Grade 3	Grade 4	Grade 5
	Expected & Unexpected	Expected & Unexpected	Unexpected	Unexpected
Unrelated Unlikely	Not required	Not required	OnCore: 30 days/quarterly ²	See SAE
Possible Probable Definite		OnCore: 30 days from end of Reporting Period ³	OnCore: 15 days from end of Reporting Period ³	
SAE ⁴	OnCore: (24-hrs), 7 days ¹			

¹ Enter into Cancer Center database within 24 hours and submit supporting documentation within 7 days.
² Data to be entered within 30 days of the end of the reporting period or the next quarterly deadline, whichever comes last. Deadlines are Jan. 31, Apr. 31, July 31, and Oct. 31.
³ Reporting is not required if AE onset is > 30 days after the last dose of study supplement
⁴ Any AE that is an SAE must be reported using the SAE timeline regardless of grade or attribution.

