9.2.3 Additional reporting Requirements

9.2.3.1 Target Adverse Events

Target AEs are AEs of special interest and will be collected throughout the treatment phase, regardless of expectedness, severity, or attribution. They are listed in [Section 6.3](#). Target AEs will not be collected during the follow-up reporting periods unless the AEs otherwise meet the DSMC or IRB reporting requirements outlined in [Sections 9.2.1](#) and [9.2.2](#).

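### Stopping the supplement early moves a subject to follow-up, where no ANC is scheduled, so recovery days for the co-primary endpoints can go uncollected; 4.7.4 and 4.9 also conflict for a first related grade 3-4 AE in Cycles 3-4

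*Combined protocol and SAP*

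**What the plan says.** **Status after stopping.** After its list of reasons, section 4.9 states: "If a subject discontinues protocol therapy for any of the above reasons, the subject will be considered" off-treatment and on follow-up. Section 4.1 dates the start of follow-up: "Early discontinuation of protocol therapy: same as off-treatment date". The off-treatment date is the day after the last dose.

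**What is collected in each phase.** Section 6.3 requires ANCs during the Treatment Phase: on Day 1 of Cycles 2-4, at weekly visits, and at least twice weekly (no more than 96 hours apart) once the count starts to fall. In Table 3 the Follow-up column is marked only for adverse event review, and its footnote reads "Subjects must be followed for 30 days following the last study intervention for AEs and for 6 months for SAEs". Section 6.4 agrees: "All subjects will be followed for a minimum of 30 days after the last dose of protocol therapy (genistein/placebo) to assess for AEs". It adds SAEs, related grade 3-4 AEs, progression, second malignancy and death to six months. Section 9.2.3.1 says "Target AEs will not be collected during the follow-up reporting periods", unless they meet other reporting thresholds.

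**What the endpoints need.** Section 8.1 has two co-primary endpoints: (a) the average recovery day over Cycles 1 and 2, and (b) the genistein-cycle average minus the placebo-cycle average. Section 7.1 defines the recovery day from the ANC series, including cycles whose nadir never falls below 500. Under 4.10, dosed subjects are not replaced and standard care continues. Sections 8.1-8.4 give neither an analysis population nor a rule for a missing recovery day.

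**First related grade 3-4 AE in Cycle 3 or 4.** Section 4.7.4 has the supplement suspended and then resumed at the prior dose after resolution. Section 4.9 lists a related AE of grade 3 or higher in those cycles as a reason to end protocol therapy.

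**The concern.** Several of the 4.9 reasons need not end chemotherapy: missed doses, a second soy exposure, unblinding, the subject's own choice, a related AE. For these subjects the count still falls and recovers in each remaining cycle, and blood counts may well be drawn in routine care, yet nothing in the protocol asks for them to be recorded.

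A stop in Cycles 1-2 can leave (a) incomplete and (b) missing. A stop in Cycles 3-4 affects (b) only. Some of these reasons may be related to treatment or outcome, so the subjects left in the analysis may no longer be comparable by arm. The 10% allowance in 8.2 addresses numbers, not comparability.

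The conflict between 4.7.4 and 4.9 is a separate defect with a bearing on the same data. A suspended subject still has ANCs scheduled; a discontinued one does not. Sites that read the two sections differently would generate different data for (b) after the same event.

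**Working it through.** **1. Does follow-up supply recovery days by another route?**

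| Possible route | What the protocol says | What it gives |
|---|---|---|
| Scheduled ANC | Table 3 and 6.4 list none in follow-up | Nothing |
| Target AEs, including neutropenia | 9.2.3.1 generally stops their collection | Nothing by itself |
| Grade 4 neutropenia as an AE | In 9.2.1, "expectedness is defined in relationship to treatment with the investigational agent". Section 5.1.7 names abdominal pain as the only expected AE, so grade 4 neutropenia is unexpected and reportable under Table 6. In 9.1.1, "Reporting will include, at minimum, the dates of onset and resolution" | Some dates, depending on when blood happens to be drawn |
| Cycle with nadir of 500 or more | Recovery day comes only from the ANC series (7.1); no grade 4 event arises | Nothing |

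The cut-off is also unclear. Table 6 starts after the subject's "last cycle taking the study supplement until 6 months post-treatment", which suggests that the stopping cycle is finished under Treatment Phase rules, whereas 4.1 and 4.9 change status at once.

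**2. The plan's own power figure.** Inputs from 8.2: 22 per arm, Poisson mean 16.25 against 13.25, one-sided 5% Mann-Whitney-Wilcoxon test. Simulation with 40,000 trials per row (tie-corrected normal approximation, no continuity correction; Monte Carlo standard error about √(0.8 × 0.2 / 40,000) = 0.002) gives 0.800, which matches the stated 80%. Type I error is 0.049. Accrual also reproduces: 44 / 0.9 = 48.9, so 49-50.

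**3. Fewer evaluable subjects for (a).** No stopping rate is given, so these losses are assumptions.

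| Evaluable per arm | Total loss from 50 accrued | Power |
|---|---|---|
| 22 | (50 − 44)/50 = 12% | 0.800 |
| 20 | (50 − 40)/50 = 20% | 0.767 |
| 18 | (50 − 36)/50 = 28% | 0.723 |

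A separate run with the continuity correction gave 0.762 at 20 and 0.719 at 18. The allowance absorbs the first losses: 50 × 0.9 = 45, or 22.5 per arm.

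**4. Keeping stoppers in, as randomised, 22 per arm.** Two assumed means for genistein-arm stoppers: the full placebo mean of 16.25 (worst case), or one exposed and one unexposed cycle, (16.25 + 13.25)/2 = 14.75.

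| Genistein arm stopping | Stoppers at 16.25 | Stoppers at 14.75 |
|---|---|---|
| 10% | 0.714 | 0.757 |
| 20% | 0.620 | 0.722 |

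With half the effect kept, power is close to that from leaving out about the same share of both arms (0.767 and 0.723). In the worst case it is lower.

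**5. Endpoint (b).** Power cannot be computed, because no within-subject variance is given.

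**6. The AE rules side by side.** Table 1 of 4.7.4 says to suspend for an initial grade 3-4 event, and the text beneath it returns the subject to the prior dose. Table 2 of 4.7.4 runs to the end of Cycle 4, so the section covers Cycles 3-4. Section 4.9 names the same event in those cycles and makes no exception for a first occurrence. Both cannot be followed.

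**The case against.** Five points can be made for the plan.

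- **Capture may be better than it looks.** Section 9 asks for a new AE entry when severity changes, and a move from grade 4 to grade 3 is the 500 threshold that defines recovery. This stands in part. But 9.1.2 opens a new record only on worsening severity or a changed relationship to the supplement, Table 6 does not require unrelated grade 3 events, and neither provides twice-weekly sampling or helps a cycle with nadir of 500 or more.
- **The Procedure Manual is unseen.** It holds the Roadmaps and data-capture detail and may close the gap. That limits the claim to what the protocol requires, but the protocol's own status rules and schedule point the other way.
- **The power figures may overstate the loss.** They follow 8.2 in treating (a) as a single Poisson draw, whereas 8.1 defines it as a two-cycle average. If the two cycles were independent (an assumption), power would be about 97%, 95-96% and 94% at 22, 20 and 18 per arm. This stands: 72% at 18 is the low end of a 72-94% range.
- **The fix saves no power and does not restore (b).** True. In a pilot that aims to estimate, as-randomised against on-supplement is partly a choice of estimand. That is a reason to state the choice; without the data the as-randomised version is not available.
- **A suspension might itself count as off-treatment.** Section 4.1 defines that date broadly, as the end of supplement for any reason. But it ties the start of follow-up to completion or to a reason listed in 4.9, so a suspension under 4.7.4 remains in the Treatment Phase.

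**Conclusion.** Both parts hold. On the protocol as written, a subject who discontinues under 4.9 leaves the only phase in which ANCs are scheduled, and recovery days for the remaining study cycles can go uncollected. The clearest gaps are cycles with nadir of 500 or more, and sampling frequency in every other cycle. The stated power and accrual are correct and are not in dispute.

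The size depends on a stopping rate that the documents do not give. On the plan's single-draw model, power for (a) falls from about 80% to 76-77% at 20 evaluable per arm or 72% at 18; it is higher throughout if averaging over two cycles reduces the variance. The main cost is to the randomised comparison rather than to power. No rate, direction or amount of bias is claimed.

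Sections 4.7.4 and 4.9 contradict each other for a first related grade 3-4 AE in Cycle 3 or 4. No view is offered on which clinical rule is right. Both points should be corrected, because counts not recorded at the time may not be recoverable later.

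**What to change.** - **Sections 4.9 and 6.4.** For subjects who discontinue protocol therapy but stay on study, keep recording ANC from routine blood counts, G-CSF use and chemotherapy dates for the remaining planned study cycles. Where the regimen no longer meets Inclusion Criterion 5, record through the last cycle that still fits the eligible pattern. Flag any recovery day that follows a gap of more than 96 hours between counts. State when Treatment Phase collection ends within the stopping cycle, so that 4.1, 4.9 and Table 6 agree.
- **Section 8.4.** Analyse (a) in all dosed subjects as randomised, with an on-treatment sensitivity analysis. Report the subjects missing from (b) by arm, with reasons.
- **Sections 4.7.4 and 4.9.** Reconcile the two instructions for a first related grade 3-4 AE in Cycles 3-4. The clinical choice belongs to the investigators.

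The cost is a short amendment and data entry of counts already drawn for care, with no added procedures. There are two drawbacks. Counts after stopping may be sparser than twice weekly and so date recovery late. The as-randomised analysis may also dilute the effect: power for (a) would be about 71% or 62% if 10% or 20% of the genistein arm stopped and had the full placebo mean, and about 76% or 72% if they kept half the effect. The gain is that (a) keeps every dosed subject in the randomised comparison.

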4.10 Withdrawal from Study

Subjects may withdraw or be withdrawn from study at any time for any of the following reasons:

- Subject decides to withdraw from study
- Discretion of the investigator
- Death

The primary reason for discontinuation or withdrawal from protocol therapy or study must be recorded in both the study and medical records, including an explanation if removed due to an investigator's discretion. All subjects that discontinue or withdraw from the study will continue to receive standard of care treatment.

A subject's participation is considered completed when the subject has received all study procedures and has completed all follow-up visits. Subjects that discontinue from the study prior to receiving any dose of protocol therapy (genistein or placebo) will be replaced. A subject who is withdrawn or discontinues from the study after receiving protocol therapy (genistein/placebo) is considered a discontinuation and will not be replaced.

5 SUPPLEMENT INFORMATION

5.1 Genistein

5.1.1 Chemical Name

5, 7-dihydroxy-3-(4-hydroxyphenyl)-4H-1-benzopyran-4-one

5.1.2 Other Names

i-cool tablets containing 30 mg geniVida™ TG (Product code 5011590)

5.1.3 Classification

Plant derived estrogen-like compound, Isoflavone

5.1.4 Molecular Formula

C₁₅H₁₀O₅

